1.1 Synopsis

| | |
|-------------------------|-----------------------------------------------------------------------------------------------------------------------------------------------------------------------------------------------------------------------------------------------------------------------------------------------------------------------------------------------------------------------------------------------------------------------------------------------------------------------------------------------------------------------------------------------------------------------------------------------------------------------------------------------------------------------------------------------------------------------------------------------------------------------------------------------------------------------------------------------------------------------------------------------------------------------------------------------------------------------------------------------------------------------------------------------------------------------------------------------------------------------------------------------------------------------------|
| Short Study Title | Australian National Vulvar Cancer Trial |
| Full Study Title | A phase II randomised clinical trial of ultrasound groin monitoring versus groin lymph node dissection to de-escalate the extent of surgery in vulvar cancer |
| Protocol Identification | ANVU |
| Development Phase | Phase II |
| Indication | Vulvar Cancer – Clinical Stage 1 or 2 |
| General aim | This clinical trial will determine whether groin ultrasound monitoring (USM) is (1) effective and safe to replace invasive groin lymph node dissection (LND) to manage vulvar cancer; and (2) decreases the morbidity and its cost associated with vulvar cancer surgery, without compromising survival. |
| Study Objectives | 
Primary objective:
 
 To determine the incidence of palpable, fixed to skin and histologically positive groin nodes at 12 months in women with vulvar cancer randomised to serial high-resolution groin USM versus standard surgical groin LND 
Secondary objectives:
 
 Compare Patient Reported Outcomes (PROMS) and Health-Related Quality of Life (HRQL) between the groups Compare pain and adverse events (morbidity) between the groups Compare lower limb lymphoedema between the groups Compare cost and cost effectiveness between the groups Determine the diagnostic accuracy of pre-operative, standardised high-resolution groin ultrasound to identify groin node metastasis. 
Translational research objective:
 
 To assess the role of blood and tissue molecular biomarkers to accurately determine the burden of disease (positive lymph nodes) in vulvar cancer, assist with risk stratification and aid disease surveillance |
| Study Endpoints | 
Primary endpoint:
 
 Incidence of clinically palpable, fixed to skin and histologically positive groin lymph nodes (node metastasis) at 12 months after surgical excision of the primary vulvar tumour |

| | |
|-------------------------------|--------------------------------------------------------------------------------------------------------------------------------------------------------------------------------------------------------------------------------------------------------------------------------------------------------------------------------------------------------------------------------------------------------------------------------------------------------------------------------------------------------------------------------------------------------------------------------------------------------------------------------------------------------------------------------------------------------------------------------------------------------------------------------------------------------------------------------------------------------------------------------------------------------------------------------------------------------------------------------------------------------------------------------------------------------------------------------------------------------------------------------------------------------------------------------------------------------------------------------------------------------------------------------------------------------------------------------------------------------------------------|
| | 
Secondary endpoints:
 
 • Health-Related Quality of Life (HRQL) and Patient Reported Outcomes (PROMS) as measured by the EQ-5D and FACT-V at baseline, 8 weeks, 6 months, and 12 months • Morbidity at 12 months after surgery • Lower limb lymphoedema incidence up to 12 months after surgery • Cost and cost effectiveness at 12 months post-surgery • Clinical accuracy of high-resolution serial ultrasound to predict groin lymph node involvement • Disease free and overall survival 12 months post-surgery 
Translational research endpoints:
 
 • Utility of biomarkers to reliably reflect the presence or absence of positive groin lymph nodes. • Explore novel biomarkers for vulvar cancer |
| 
Translational research
 | 
All participants (pending consent) will be asked to donate blood samples and Formalin-Fixed Paraffin Embedded (FFPE) tissue (vulvar tissue with/without lymph nodes) to be banked for the purpose of future molecular and biomarker research.
 
Tumour with/without groin lymph nodes will be collected at the diagnostic biopsy procedure and/or during surgery. Throughout the study, clinical trial coordinators at each site will arrange for blocks for each episode of biopsy or excision to be extracted (vulvar tissue, lymph nodes) and couriered to a central laboratory in QLD in batches as required and will undergo centralised histopathology review.
 
For participants who receive standard upfront groin LND, blood will be collected at two time points: prior to surgery (baseline) and 8 weeks post-surgery. For participants who have serial high-resolution groin USM, blood will be collected prior to surgery (baseline) and at each ultrasound scan (7-time points total). Blood samples will be processed and stored at local labs, and then couriered to a central laboratory in QLD in batches as required. Specimens will be stored for an indefinite period following the last participant completing the trial.
 
All translational research using these samples will be subject to a separate ethics application.
 |
| 
Study Design
 | 
A phase II, open label, domestic and international, three-group, randomised clinical trial.
 |
| 
Randomisation
 | 
Participants with a normal/negative baseline groin node ultrasound will be randomised 2:1 to receive radical wide local excision or radical vulvectomy with either:
 |

| | |
|-------------------------------------------------------|--------------------------------------------------------------------------------------------------------------------------------------------------------------------------------------------------------------------------------------------------------------------------------------------------------------------------------------------------------------------------------------------------------------------------------------------------------------------------------------------------------------------------------------------------------------------------------------------------------------------------------------------------------------------------------------------------------------------------------------------------------------------------------------------------------------------------------------------------------------------------------------------------------------------------------------------------------------------------------------------------------------------------------------------------------------------------------------------------------------------------------------------------------------------------------------------------------------------------------------------------------------------------------------------------------------------------------------------------------------------------------------------------------------------------------------------------------------------------------------------------------------------------------------------------------------------------------------------------|
| | 
 • bilateral groin USM every 2 months (groin lymph nodes are not removed) in conjunction with clinical examinations every 3 months for a period of 12 months 
OR
 
 • groin LND (based on clinical standards: either a sentinel node biopsy (SNB) or an inguinofemoral lymph node dissection (IFL)), 
Randomisation will be stratified by clinical stage, HPV status, Charlson Comorbidity Index, and histological cell type.
 |
| 
Eligibility Criteria (Inclusion and Exclusion)
 | 
Inclusion Criteria:
 
 • Females, over 18 years, with histologically confirmed squamous cell carcinoma (SCC), adenocarcinoma, or melanoma of the vulvar • Clinically stage 1b or 2 on medical imaging (CT or MRI scan of pelvis, abdomen, and chest), without evidence of regional or distant metastatic disease • Willing to undergo IFL/SNB according to local clinical practice management guidelines • Willing and able to comply with all study requirements, timing and/or nature of required assessments • Signed written informed consent • Negative (serum or urine) pregnancy (BHCG) test \leq 30 days of surgery ONLY in pre-menopausal women and women $<$ 2 years after the onset of menopause 
Exclusion Criteria:
 
 • Women with non-invasive vulvar conditions (e.g. non-invasive non-mammary Paget’s disease) • Squamous cell carcinoma (SCC) of the vulvar with depth of invasion \leq 1 mm • Clinical or medical imaging evidence of regional and/or distant metastatic disease • Serious concomitant systemic disorders incompatible with the study (at the discretion of the investigator) • Other prior malignancies $<$ 5 years before inclusion, except for successfully treated keratinocyte skin cancers, or ductal carcinoma in situ • Estimated life expectancy \leq 6 months |
| 
Study intervention
 | 
Eligible women (n=240) will receive a bilateral groin node ultrasound up to 30 days prior to planned surgery.
 
 • If the groin node ultrasound is suspicious/indeterminate, the participant will receive an upfront full groin LND or SNB, which is current standard treatment (according to local clinical practice management guidelines; estimated n=60). |

| | |
|-------------------------------------------------|---------------------------------------------------------------------------------------------------------------------------------------------------------------------------------------------------------------------------------------------------------------------------------------------------------------------------------------------------------------------------------------------------------------------------------------------------------------------------------------------------------------------------------------------------------------------------------------------------------------------|
| | 
 If the groin ultrasound is negative/normal (n=180), participants will be randomised 2:1 to receive either a groin LND (n=60) or bilateral groin USM every 2 months along with clinical examination every 3 months for a period of 12 months (n=120; no upfront groin LND). 
All participants will receive appropriate surgical excision of the primary tumour (radical wide local excision or radical vulvectomy). All lymph nodes will undergo central pathology review [1]. Postoperative treatment will follow local institutional treatment guidelines.
 |
| 
Stage details and number of participants
 | 
240 participants in total:
 
 Ultrasound negative/normal groin nodes (120 undergoing groin USM every 2 months along with clinical examination every 3 months and 60 upfront groin IFL/SNB) Ultrasound suspicious/indeterminate groin nodes (60 having upfront groin IFL/SNB) |
| 
Study Duration
 | 
Enrolment for this study is projected to conclude within a 4-year timeframe. The study will be deemed complete once 180 participants have been enrolled, randomised, and successfully completed a 12-month follow-up period.
 |

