5.4 Secondary Objective

1. Compare Patient Reported Outcomes (PROMs) and Health Related Quality of Life (HRQL) between the groups
2. Compare pain and adverse events (AEs) (morbidity) between the groups
3. Compare incidence of lower limb lymphoedema at 12 months post-surgery between the groups
4. Compare cost and cost effectiveness between all groups
5. To assess the role of molecular biomarkers to accurately determine the burden of disease (positive lymph nodes) in vulvar cancer, assist with risk stratification and aid disease surveillance
6. Determine the diagnostic accuracy of pre-operative, standardised high-resolution groin ultrasound to identify groin node metastasis.

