5.6 Secondary Endpoint

1. HRQL and PROMS as measured by the EQ-5D and FACT-V at baseline, 8 weeks, 6 months, and 12 months
2. Morbidity at 12 months after surgery
3. Lower limb lymphoedema: incidence up to 12 months after surgery
4. Cost and cost effectiveness at 12 months post-surgery
5. Clinical accuracy of high-resolution ultrasound to predict groin lymph node involvement
6. Disease-free survival (DFS) and overall survival (OS)
7. Utility of biomarkers to reliably reflect the presence or absence of positive groin lymph nodes
8. Explore novel biomarkers for vulvar cancer

6. Study Design

A phase II, open label, multicentre, three-group, randomised clinical trial (ANVU).

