6.4 Randomisation

Eligible participants will be required to provide signed informed consent before being enrolled. Prior to enrolment, each patient will be screened for eligibility according to the inclusion and exclusion criteria. Participants will then receive a bilateral groin node ultrasound, participants who are found to have negative groin nodes will be randomised using a secure online randomisation system 2:1 to groin USM vs standard groin LND:

- ~120 participants will receive radical wide local excision or radical vulvectomy with serial high-resolution bilateral groin USM every 2 months in conjunction with clinical examinations every 3 months (groin lymph nodes are NOT removed).
- ~60 participants will receive radical wide local excision or radical vulvectomy with groin LND (Based on local clinical practice management guidelines.: either a SNB or an IFL).

Randomisation will be stratified by:

- Clinical stage
 - Depth of invasion (1-2 mm)
 - Depth of invasion (2.1-3 mm)
 - Depth of invasion 3.1 + mm
- HPV status
 - HPV positive
 - HPV negative
- Charlson Comorbidity Index ($<$ 5, \geq 5)

- Histological cell type
 - SCC
 - All other cell types (i.e. adenocarcinoma, melanoma).

Participants with a groin node ultrasound that is suspicious/indeterminate will not be randomised but receive standard groin LND (SNB or IFL as appropriate, as per institutional guidelines).

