7.5 Follow-Up (Visits 4-9)

All enrolled participants, irrespective of treatment group will be followed-up for 12 months. Participants without groin LND will be provided with medical imaging request forms to receive groin ultrasound examinations every 2 months. **Changes in ultrasound patterns from “normal” to “suspicious” will alert the gynae-oncologist and trigger further clinical action, such as groin LND and histological assessment of the groin nodes. Groin USM will not be offered to women who had a groin LND (IFL or SNB) as it is not standard practice for these patients.** If ultrasound scan surveillance following sentinel node biopsy is included in the standard care protocol at any of the study sites, participants randomised to lymph node dissection (LND) can undergo ultrasound scans as part of their standard care, though it is not mandatory for this study.

Participants will be assessed for local, regional, or distant recurrence, quality of life status, and treatment morbidity for 12 months. Data collected will include documentation of the status of disease, AEs, pain level, health status, quality of life and lymphoedema.

Participants randomised to serial groin USM will be seen every 3 months by a gynaecological oncologist or gynaecologist for clinical examination as per routine standard. Participants receiving standard groin LND (either SNB or LND) will be seen at 8 weeks, 3, 6, 9 and 12 months as per standard clinical practice. Follow up will be handed over to the treating gynaecological oncologist after 12 months.

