11.2.4 Lower Limb Lymphoedema

Lymphoedema will be self-assessed using validated questionnaires successfully used in our previous studies [16]. We will use our previously developed self-reported lymphoedema tool (questions on swelling in legs, pelvis or vulvar; 14 lower-limb symptoms including pain, tingling, weakness) to analyse lymphoedema at 8 weeks, and 6 months, and 12 months.

We will compare the prevalence of subjective symptoms of lymphoedema over time using a general linear mixed modelling approach. Similar analyses will be conducted on the subgroup of patients for whom we have objective assessment of lymphoedema (using leg measurements).

11.2.5 Determine the Clinical Accuracy of Preoperative, Standardised, High-Resolution Ultrasound to Identify Vulvar Cancer Patients with Positive (Involved) Groin Nodes

In women who receive a groin LND, overall ultrasound assessment scores will be compared to histopathology of the groin nodes. Sensitivity, specificity, positive and negative predictive values of the ultrasound outcomes compared to histopathology, will be evaluated together with receiver-operating characteristic.

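### Accuracy of serial ultrasound is listed as a secondary endpoint, but the only accuracy analysis covers the pre-operative scan and cannot deliver it

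*Protocol*

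**What the plan says.** The accuracy question appears in five places in the protocol.

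- Synopsis, study objectives, and section 5.4 item 6: "Determine the diagnostic accuracy of pre-operative, standardised high-resolution groin ultrasound to identify groin node metastasis".
- Synopsis, secondary endpoints: "Clinical accuracy of high-resolution serial ultrasound to predict groin lymph node involvement".
- Section 5.6 item 5: "Clinical accuracy of high-resolution ultrasound to predict groin lymph node involvement", with neither serial nor pre-operative.
- Heading of section 11.2.5: "Determine the Clinical Accuracy of Preoperative, Standardised, High-Resolution Ultrasound to Identify Vulvar Cancer Patients with Positive (Involved) Groin Nodes".
- Text of section 11.2.5, which fixes the analysis set and the reference: "In women who receive a groin LND, overall ultrasound assessment scores will be compared to histopathology of the groin nodes".

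The design determines who has histology. The USM arm is described in the synopsis as "n=120; no upfront groin LND", and section 6.4 repeats that "groin lymph nodes are NOT removed". Under section 7.5, a scan that turns from normal to suspicious will "trigger further clinical action, such as groin LND and histological assessment of the groin nodes". Sections 6.5.3 and 7.5.2 add that other concerning findings, including those at clinical examination, can lead to LND, and that a woman with such findings may instead continue monitoring. Section 7.5 does not offer trial USM to women who have had LND, although sites may scan them as part of standard care.

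**The concern.** The pre-operative scan and serial monitoring are different index tests. The first decides who is randomised. The second is the strategy being randomised. An endpoint about the second, with an objective and an analysis only about the first, cannot be reported as written.

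Two things could go wrong. First, the section 11.2.5 method might be carried over to serial scans because it is the only one available. It would then include mainly women whose monitoring had already flagged a node, so the test result would largely decide who is counted. Second, the pre-operative figure might be quoted as evidence on monitoring. Section 4 promises to affirm the accuracy of ultrasound without saying which use is meant, which leaves room for that.

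The wording of section 11.2.5 also affects the pre-operative estimate. It admits women who receive a groin LND, not women who receive one upfront. A USM woman whose node is found during surveillance and who then has LND could enter. She would be a false negative for the pre-operative scan and a true positive for serial monitoring.

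**Working it through.** **1. The index test, place by place**

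| Place | Index test named |
|---|---|
| Synopsis, objectives | pre-operative scan |
| Synopsis, secondary endpoints | serial ultrasound |
| 5.4 item 6 | pre-operative scan |
| 5.6 item 5 | no timing |
| 11.2.5 heading | pre-operative scan |

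The synopsis endpoint has no objective and no analysis with the same index test.

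**2. The protocol's own figure for serial accuracy**

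Section 3.4 reports, from a pilot of 32 women, sensitivity 100% (44–100%), specificity 97% (83–99%) and negative predictive value 100% (88–100%). Counting women and using Wilson 95% intervals:

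- Sensitivity 3/3: 100% (43.9–100%)
- Specificity 28/29: 96.6% (82.8–99.4%)
- Negative predictive value 28/28: 100% (87.9–100%)

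The figures reproduce. The denominators cover the whole cohort (3 + 29 = 32), so women without node removal must have been counted. The protocol does not state how their negative status was established.

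**3. How many USM women section 11.2.5 could score**

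Inputs: 120 USM women (synopsis) and the pilot share reaching LND, which is assumed to carry over. Section 3.4 leaves that share unclear. It says 29 women could be spared LND (3/32), its specificity implies one false positive (4/32), and it mentions two nodes removed and found negative (up to 5/32).

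| Assumed LND share | LND among 120 | No LND histology |
|---|---|---|
| 3/32 | 120 × 3/32 = 11.3 | 108.8 (91%) |
| 4/32 | 120 × 4/32 = 15.0 | 105.0 (88%) |
| 5/32 | 120 × 5/32 = 18.8 | 101.3 (84%) |

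**4. What the restriction does to serial accuracy (illustration at 4/32)**

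Expected counts in 120 women: true positives 120 × 3/32 = 11.25; false positives 120 × 1/32 = 3.75; true negatives 120 × 28/32 = 105; false negatives 0.

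- All 120 women, with follow-up as the reference for those not operated on: specificity 105/(105 + 3.75) = 96.6%; negative predictive value 105/105 = 100%.
- Only women with LND, if all reach it through a suspicious scan: sensitivity 11.25/11.25 = 100%; specificity 0/3.75 = 0%; negative predictive value 0/0.

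At 3/32 there are no LND-negative women, and specificity also has no denominator.

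**5. These are limiting values**

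LND can follow an examination finding after normal scans. Section 11.1 anticipates a 3% recurrence probability, or 120 × 0.03 = 3.6 women. If between none and all of them had only normal scans and then LND, sensitivity runs from 100% down to 11.25/(11.25 + 3.6) = 75.8%.

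**6. Crossovers in the pre-operative estimate**

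Assume that 3/32 of scan-negative women are node-positive.

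- The 60 women randomised to LND: negative predictive value (60 × 29/32)/60 = 54.4/60 = 90.6%.
- Adding the 15 crossovers of step 4 (11.25 positive, 3.75 negative): (54.4 + 3.75)/75 = 58.1/75 = 77.5%.

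The reading of one phrase moves the result by about 13 percentage points. The second figure takes in the flagged USM women and leaves out the other 105.

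**The case against.** The strongest reply is that section 11.2.5 is headed as a pre-operative analysis, matches the stated objective, and never claims to analyse serial scans. On that view the synopsis contains one stray word, and any serial analysis may be left to the statistical analysis plan announced in section 11.2. The heading point stands: section 11.2.5 addresses a different question and should not be called a faulty method for serial accuracy. The deferral does not settle the matter. The protocol fixes conflicting index tests and an LND-only analysis set, so a plan that follows section 11.2.5 cannot deliver the synopsis endpoint, and one that delivers the endpoint must go beyond it.

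A reader might infer that serial sensitivity is bound to be 100% and specificity 0% whatever the true accuracy. The documents do not support that. Sections 6.5.3 and 7.5.2 allow LND after examination findings, so test-negatives with histology would be few, not necessarily zero. The number of LND-negative women is not established either, because section 3.4 says that 29 of 32 could be spared LND and that a false positive was determined after negative needle cytology.

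A reader might also infer that monitoring goes unassessed. It does not. Its main failure, palpable and histologically positive groin nodes by 12 months, is the primary endpoint and is analysed in the USM arm (sections 11.1 and 11.2.1).

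Finally, deleting one word would align the text. That is a legitimate choice if serial accuracy is not meant to be estimated.

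**Conclusion.** The point holds as a contradiction between a stated secondary endpoint and the rest of the protocol. Serial accuracy is listed, but no analysis can deliver it. The one accuracy analysis would leave about 84–91% of the USM arm unscored if used for that purpose, and would score a group selected mainly by a positive test. The direction of the distortion is clear. The exact 100% and 0% are limits.

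The coverage figures assume that pilot LND shares carry over. The pilot had 32 women, and section 3.4 describes its scan interval as both three-monthly and two-monthly. Most of the arm stays unscored at any LND share below 50%, and avoiding LND in most women is the trial's premise. The 13-point shift from crossovers is an illustration under the assumptions in step 6, and it arises only if section 11.2.5 is read as including later LND.

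This is a secondary endpoint. The primary safety rule and the stopping rule are not affected. The change should be made, but the trial's main conclusion does not depend on it.

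**What to change.** Align the synopsis objective and endpoint, sections 5.4 and 5.6, and section 11.2.5, and state two endpoints that are not pooled.

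- **(a) Pre-operative scan.** Compare with node histology in women who have upfront LND. Writing upfront into section 11.2.5 keeps later USM crossovers out.
- **(b) Serial monitoring.** Analyse per woman, in all women randomised to USM. Test-positive means any suspicious or indeterminate surveillance scan. The reference is histology where obtained and otherwise groin status at 12 months. Groin metastases that appear after only normal scans count as false negatives.

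For (b), state that 12-month follow-up is a weaker reference than histology and that verification differs by scan result, since flagged women are the ones most likely to have histology.

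If the sponsor does not intend to estimate serial accuracy, delete the word serial from the synopsis endpoint and do not quote the pre-operative figure for serial monitoring.

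The cost is protocol and analysis-plan wording plus one further table. The scans, histology and 12-month disease status are already collected. The downside of (b) is its mixed reference standard, which has to be reported with the estimate.

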11.1 Sample Size & Stopping Rules

Incurable groin recurrence has a >90% mortality within 12 months [21]. We estimate the probability of incurable groin recurrence within 12-month of an upfront LND, i.e., $P(\text{recur}|\text{LND})$, to plausibly be up to 3% in usual practice. This is based on a 32% prevalence of positive nodes in clinical stage I/II vulva cancer [41] and that the false negative rate for routinely used SNB is up to 8.8% [7,42]. A

recurrence probability given groin USM, i.e., $P(\text{recur}|\text{USM})$, of 6% would be acceptable to avoid the side-effects of LND based on our decision analysis using best available evidence, expert judgement, and consumer input. $P(\text{recur}|\text{USM})$ will be characterised using a Bayesian Beta-Binomial model with priors informed by our pilot study (1/32 recurrences) [10]. We will declare groin USM acceptably safe if the probability that $P(\text{recur}|\text{USM}) < 0.06$ is 80%. A Bayesian Monitoring approach will ensure participant safety (MD Anderson Biostatistics BTOX routine www.trialdesign.org/#software). Stopping early due to unacceptably safety will be triggered if there is more than a 70% probability that $P(\text{recur}|\text{USM})$ exceeds 0.06 (i.e., recurrence rate of at least 5/40, 6/60, 7/80, 9/100, or 10/120). We anticipate that $P(\text{recur}|\text{USM})$ is truly 3% and thus calculate that ANVU has less than a 2% probability of incorrectly stopping early for unacceptable safety and a 0.85 probability of correctly declaring acceptable safety at N=120. The statistical design accommodates expansion beyond N=120 USM participants (e.g., as a protocol amendment) if neither safety criterion is reached and the predicted probability of success given expansion is at least 80%.

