11.2 Statistical Analysis

Analyses will adhere to the intention-to-treat principle and a Statistical Analysis Plan will be prepared using the estimand framework (ICH E9-R1 addendum).

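### The end-of-study rule needs 180 randomised women to complete 12 months, but only 180 are to be randomised, with no allowance for death or loss

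*Protocol*

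**What the plan says.** Under Study Duration in section 1.1, the Protocol says: "The study will be deemed complete once 180 participants have been enrolled, randomised, and successfully completed a 12-month follow-up period". It does not define successful completion.

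The Study intervention row of the same synopsis uses the same figure for the number to be randomised: "If the groin ultrasound is negative/normal (n=180), participants will be randomised 2:1 to receive either a groin LND (n=60", with the other 120 allocated to USM. Section 6.4 repeats about 120 and about 60.

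Four other places bear on the rule:

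- Section 11.1 describes the primary event as lethal: "Incurable groin recurrence has a >90% mortality within 12 months". It sets the safety decision at 120 USM participants. Going beyond 120 is a separate option, open only if neither safety criterion is reached and the predicted probability of success is at least 80%.
- Section 11.2 says: "Analyses will adhere to the intention-to-treat principle".
- Section 6.5.3 removes USM women who do not keep to the scan and examination schedule, and section 12.7 allows removal after missed visits. Neither says whether outcome data on removed women are kept. By contrast, sections 6.5.3 and 10.6.5.1 do keep data on women with suspicious or positive nodes.
- Section 7.5 says: "All enrolled participants, irrespective of treatment group will be followed-up for 12 months".

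**The concern.** A completer target equal to the planned number randomised can be met in two ways only: nobody dies, withdraws, is lost or is removed, or more than 180 women are randomised. The first is very unlikely. The primary event is itself expected to kill, eligibility excludes only a life expectancy of 6 months or less (section 6.3), and the USM arm has its own removal route. The second contradicts the planned sample size and takes the USM arm past the number at which section 11.1 states its operating characteristics.

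The sentence also leaves open which women make up the 120 in the safety decision. Non-completion is likely to be related to the primary event, so it matters whether non-completers stay in the count. In an open-label trial the question should not be settled late, when outcomes are known.

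**Working it through.** **Inputs.** From section 1.1: 180 completers required, 180 randomised (120 + 60), 240 enrolled. From section 11.1: "priors informed by our pilot study (1/32 recurrences"), a safe declaration when the posterior probability of a rate below 0.06 is 80% (taken as at least 80%), stopping when the probability of a rate above 0.06 exceeds 70%, and an assumed true rate of 3%. The Protocol gives no non-completion rate and no share of events in women who fail to complete; both are assumptions below.

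**1. Reproduce the stated design.** The weight given to the pilot is not stated. Beta(0.5, 15.5), the pilot at half weight, and Beta(1.5, 31.5), the pilot added to Beta(0.5, 0.5), both return the printed boundaries ("recurrence rate of at least 5/40, 6/60, 7/80, 9/100, or 10/120"). Full weight, Beta(1, 31), does not: it gives 7/60 and 8/80. Under Beta(0.5, 15.5) the posterior probability of a rate below 0.06 is 0.874 at 5/120 and 0.770 at 6/120, so the pass limit is 5. Beta(1.5, 31.5) gives the same limit (0.859 and 0.758). With looks at 40, 60, 80, 100 and 120 and a true 3%, P(declare safe) = 0.847 (stated 0.85) and P(stop before 120) = 0.017 (stated below 0.02). At a true 6%, P(declare safe) = 0.27; at 8%, 0.08.

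**2. Can 180 randomised give 180 completers?** P(all complete) = (1 − d)^180 for non-completion rate d:

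- d = 1%: 0.16
- d = 2%: 0.026
- d = 3%: 0.004

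Deaths from the primary event alone make this hard. Assume 3% events in both arms (section 11.1 gives up to 3% after dissection), onset uniform over 12 months, and 90% mortality at 12 months after the event. If death times are uniform, the share dead by month 12 is 0.9 × 0.5 = 0.45. If they are exponential, it is 1 − 0.9/ln 10 = 0.61. P(no such death in 180) is then (1 − 0.03 × 0.45)^180 = 0.09, or (1 − 0.03 × 0.61)^180 = 0.04. With later onset and a share of 0.20, it is (1 − 0.006)^180 = 0.34.

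**3. What literal compliance would need.** Randomised = 180/(1 − d); USM = 120/(1 − d); enrolled = randomised × 240/180.

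| d (assumed) | Randomised | USM | Enrolled |
|---|---|---|---|
| 5% | 190 | 127 | about 253 |
| 10% | 200 | 134 | about 267 |

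**4. Safety rule if every randomised woman is kept.** The 80% limit was recomputed at each N, without interim stopping. At N = 127 the pass limit is 5 or 6 depending on the prior; at 134 it is 6. P(declare safe) across these cases, against N = 120:

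| True rate | N = 120 | N = 127 and 134 |
|---|---|---|
| 3% | 0.85 | 0.82 to 0.91 |
| 6% | 0.27 | 0.22 to 0.36 |
| 8% | 0.08 | 0.05 to 0.11 |

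Much of the spread comes from the whole-number limit. A simulation (40,000 runs per setting, Beta(0.5, 15.5)) randomised USM women until 120 completed, with 5% other non-completion. Mean N was about 126 to 136. P(declare safe) was 0.87 to 0.90 at 3%, 0.30 to 0.32 at 6% and about 0.09 at 8%, almost the same whether 0 or 90% of women with events failed to complete.

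**5. Safety rule if the 120 were completers.** If a share f of events falls in women who do not complete, the rate among completers is q = p(1 − f)/(1 − pf). With 120 completers, limit 5 and stopping boundaries applied:

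| True rate p | f = 0 | f = 0.25 | f = 0.50 |
|---|---|---|---|
| 6% | q = 0.060: 0.27 | q = 0.0457: 0.53 | q = 0.0309: 0.83 |
| 8% | q = 0.080: 0.08 | q = 0.0612: 0.25 | q = 0.0417: 0.62 |

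**The case against.** A reader might infer that women who die or withdraw are replaced. No section says so. The sentence describes when the study is deemed complete, and the synopsis gives fixed totals. Replacement is what the sentence would need in order to be met; it is not a stated procedure.

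A reader might also infer that the safety rule at 120 is broken and that fatal groin recurrences drop out of it. The documents point the other way. Section 11.1 counts USM participants, not completers, and section 11.2 promises intention to treat. Sections 6.5.3 and 10.6.5.1 keep data on women with suspicious or positive nodes, section 12.1 monitors groin metastases continuously, and section 12.5 adjudicates every reported recurrence. A recorded groin recurrence followed by death therefore remains an event. The rule is a posterior probability, so it can be computed at any N, and its value for a given count and N does not depend on why enrolment continued. The large increases in step 5 need events to be deleted, which nothing in the Protocol directs.

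Two further points stand. The lethality figure concerns the period after incurable recurrence, not after surgery, so the share dying before month 12 is unknown. And one might think that late-enrolled women with a suspicious ultrasound, who are not randomised, would be cut short; section 7.5 already promises 12 months to all enrolled women.

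None of this repairs the sentence. It still conflicts with the planned 180, still leaves successful completion undefined, and still pushes USM enrolment past 120 without the conditions of section 11.1. These are matters of enrolment target and end of study, which a protocol fixes itself.

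**Conclusion.** The end-of-study rule contradicts the planned sample size. With 180 randomised it will almost surely not be met: the chance is 0.16 even at 1% non-completion. Literal compliance means about 10 extra randomised women at 5% non-completion and 20 at 10%.

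The effect on the safety decision depends on who is counted. Under intention to treat it is modest: about 0.22 to 0.36 at a true 6%, against 0.27 as designed. Under a completers-only count it would be serious and would favour declaring safety (0.53 or 0.83 at a true 6%), but that is an illustration with assumed shares of lost events and not what the Protocol directs. These figures also rest on the two priors that match the printed boundaries. The point is of moderate severity: a badly fixed rule that invites outcome-related over-enrolment or a completers-only count, not a demonstrated failure of the design.

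**What to change.** Replace the Study Duration sentence in section 1.1 with: *The study is complete when 180 women have been randomised and every enrolled woman has reached 12 months after surgery, died, withdrawn consent or been lost to follow-up. Randomised women are not replaced. The N in section 11.1 is all women randomised to USM, and a groin event recorded before death, withdrawal or removal counts.*

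This costs one amended sentence, with no extra patients or procedures, and it avoids over-enrolment. Any expansion past 120 USM women then stays under the conditions of section 11.1. The downside is that some randomised women will have no month-12 visit. The change should be made before enrolment closes.
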